## **2. STATISTICAL HYPOTHESES**

There is no study hypothesis for the open-label phase of the study.

## **3. SAMPLE SIZE DETERMINATION**

### **3.1. Efficacy (Total Sample Size)**

There is no sample size determination for the open-label phase of the study.

### **3.2. Immunogenicity Subset**

In the double-blind phase, for a total of approximately 400 participants in the Immunogenicity Subset, blood will be collected for analysis of humoral immune responses before each vaccination, 28 days after the 1st vaccination and 14 days after the second vaccination.

In the open-label phase, for participants from the Immunogenicity Subset who did not receive a booster dose, blood will be collected at 6 months, 1 year, 18 months, and 2 years after the second vaccination.

All participants in the Immunogenicity Subset will be enrolled from Study Stage 2. Participants in the Immunogenicity Subset in the double-blind phase and in the open-label phase will be divided into 4 groups as presented in [Table 3](#).

**Table 3      Sample Size and Distribution of the Immunogenicity Subset Between Active and Placebo Groups**

Study Vaccine	Subset 1a	Subset 1b	Subset 2a	Subset 2b
Ad26.COV2.S ( $5 \times 10^{10}$ vp)/Ad26.COV2.S ( $5 \times 10^{10}$ vp)	50	50	50	50
Placebo/placebo	50	50	50	50
Total	100	100	100	100

vp = virus particles

Subset 1a: healthy participants  $\geq 18$  years to  $<60$  years of age without relevant comorbidities, enrolled during Stage 2.

Subset 1b: healthy participants  $\geq 60$  years of age without relevant comorbidities, enrolled during Stage 2.

Subset 2a: participants  $\geq 18$  to  $<60$  years of age with relevant comorbidities, enrolled during Stage 2.

Subset 2b: participants  $\geq 60$  years of age with relevant comorbidities, enrolled during Stage 2

All participants will have a blood sample taken at the time of the unblinding visit (before open-label vaccination) and at the Booster Vaccination Visit (before booster vaccination) for analysis of serum antibodies against SARS-CoV-2 nucleocapsid (N\_protein), regardless of whether they were part of the Immunogenicity subset in the double-blind phase.

#### 4. ANALYSIS SETS FOR ANALYSIS

Vaccine assignment will be analyzed according to the *as-treated* principle. The analysis sets that are used for the analysis of safety and immunogenicity for the open-label active phase and the open-label passive phase are described in [Table 4](#).

The safety analysis will include the data from the double-blind phase combined with the open-label active follow-up phase and will be performed using the full analysis set (FAS). The safety data collected after PA7 approval will be presented similarly but separately from the active follow-up. The analysis set used for the passive follow-up is the subset of participants of the FAS who are still active on the day that their site approves PA7 (FAS7).

Analyses of immunogenicity will be performed on the per protocol immunogenicity analysis set (PPI).

**Table 4: Analysis Sets**

Analysis Sets	Description
Enrolled	The enrolled analysis set includes all participants who signed the informed consent form (ICF) and who were not screen failures.
Randomized	The randomized analysis set includes all enrolled participants who were randomized in the study.
Full Analysis Set (FAS)	All randomized participants with at least one documented study vaccine and met inclusion criterion 1, regardless of the occurrence of protocol deviations and serostatus at enrollment.
Full Analysis Set under PA7 (FAS7)	All randomized participants that are part of the FAS that are still active once the site approves PA7.
Per Protocol Immunogenicity Analysis Set (PPI)	All randomized and vaccinated participants (receiving two doses of Ad26.COV2.S at Day 1 and Day 57), including those who are part of the Immunogenicity Subset and for whom immunogenicity data are available, excluding samples after major protocol deviations (MPD) expected to impact the immunogenicity outcomes (such as administration of COVID-19 vaccine outside the study). In addition, for participants who experience a SARS-CoV-2 event (molecularly confirmed and/or confirmed by N-serology), samples taken after the event and samples taken outside protocol windows will not be taken into account in the assessment of the immunogenicity. The PPI population is the primary immunogenicity population. For key tables, sensitivity immunogenicity analyses will also be performed on the FAS, including participants who are part of the Immunogenicity Subset for whom immunogenicity measures are available. Excluded samples might be taken into account as well in the sensitivity analysis.

The analysis sets that are used for the descriptive evaluations of efficacy in the open label active follow-up phase of the study include the participants from the full analysis set who are at risk to develop an endpoint within the observational period. These sets can be considered as risk sets. The observational period and the definition of the risk sets differ per study dose cohort. All details on the efficacy analysis risk sets are explained in Section 5.2.2. The population used for the analysis in the open-label passive follow-up phase is the full analysis set who are still active in the study at the time the site approves PA7 (FAS7). The same vaccination groups as the open-label active phase are presented.

Descriptive evaluations of efficacy will be performed on the risk set for the study cohort.

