For safety, the data of the double-blind phase and the open-label active follow-up phase are combined. Safety data for the following vaccination groups will be presented:

1. Placebo: Participants who were randomized and first vaccinated with Placebo until they received any other active COVID-19 vaccine.
2. Ad26.COV2.S: Participants whose first active vaccination is Ad26.COV2.S. Participants remain in this group (also when receiving a second dose of Ad26.COV2.S) until they receive an outside active COVID-19 vaccination.
3. Any schedule non-mRNA + Ad26.COV2.S OR any schedule mRNA + Ad26.COV2.S: Participants who first received one or more active non-mRNA COVID-19 vaccinations or one or more active mRNA COVID-19 vaccinations and who were boosted with one or more Ad26.COV2.S vaccinations
4. Mixed achedule: all other safety data and safety follow-up, including safety data following only an outside vaccine regimen, or safety data following a mixed schedule of Ad26.COV2.S and mRNA/non-mRNA vaccines.

For efficacy, the open-label phase will include 3 main study cohorts, based on the vaccination schedules received:

- Two-dose schedule cohort: participants who received the 2 doses of the Ad26.COV2.S vaccine according to initial design of the study on Day 1 and Day 57 (Visit 1 and Visit 4), regardless whether this was before or after unblinding. The number of days between

first Ad26.COV2.S vaccination and second Ad26.COV2.S vaccination must be a maximum of 70 days to qualify for the two-dose cohort.

- One-dose schedule cohort: participants who received a single dose of the Ad26.COV2.S vaccine in the context of the open-label vaccination (eg, placebo participants receiving Ad26.COV2.S vaccine during cross-over vaccination) or participants who only received one dose of Ad26.COV2.S vaccine during the double-blind phase of the study. These participants remain in this cohort until they receive the booster vaccination in the context of PA6 or an outside vaccination. Participants who will not receive a booster dose will continue in this cohort until they receive an outside vaccination.

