### **5.1.3. Participant Dispositions**

Participant information will be shown for the full analysis set by randomized treatment group and by the vaccination groups used in the safety analysis, presented in Section [5.4.4](#).

The number of participants in the following disposition categories will be summarized throughout the study by vaccination group and overall:

- participants in the FAS
- participants in the FAS7
- participants randomized
- participants vaccinated at day 1 and not randomized
- participants randomized, not vaccinated at day 1
- participants randomized and vaccinated at day 1
- participants vaccinated at day 1 with incorrect treatment
- participants vaccinated at day 1 with correct treatment
- participants who discontinued study (and reasons for discontinuation)
- participants who discontinued study before PA7 site approval

Additionally, the disposition of the efficacy risk sets (explained in Section 5.2.2) will be provided including the reasons why subjects are excluded from the risk set starting from the initial study vaccination received in the FAS. The efficacy risk set will be presented for the 1 dose cohort, 2 dose cohort and booster dose cohort. Note that subjects from the 1 dose cohort can also be included in the 2 dose or booster dose cohort and therefore can be part of multiple risk sets.

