### 5.4. Safety Analyses

All safety analyses will be performed on the FAS or FAS7.

The presentation of the safety data is divided into 2 parts, one set of tables will be created for the entire active follow-up period covering the double blind and open-label active phase until site approval of PA7 and another set of tables will be created for the passive follow-up period covering

the safety data from site approval of PA7 until study end. The first set of tables covering the active follow-up is performed on the FAS and the second set of tables covering the passive follow-up is performed on FAS7.

No formal statistical testing of safety data is planned. All safety analyses will be presented overall and no presentations by subgroups are planned.

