#### **5.4.4. Vaccination groups**

All safety analyses will be tabulated by vaccination group according to the *as treated* principle. The COVID-19 vaccinations received outside of the study are considered as well. Participants can be present in more than 1 vaccination group as described below. Safety data by vaccination group will be analyzed descriptively.

The following vaccination groups will be presented:

A. Layout 1a:

1. Placebo

All participants who received as first vaccination a placebo injection. All safety data will be reported here until the participant receives an active COVID-19 vaccination (Ad26.COV2.S or outside vaccination).

2. Ad26.COV2.S

All participants who received as first active COVID-19 vaccination Ad26.COV2.S until the participant receives an outside COVID-19 vaccination. This includes participants who initially received placebo and subsequently received Ad26.COV2.S, however only the safety data after the Ad26.COV2.S vaccination until the participant receives an outside

COVID-19 vaccination (if applicable) will be presented here. The safety data of participants who received 2 or more Ad26.COV2.S vaccinations will be presented by post-dose 1, post-dose 2, etc.

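### Minor: the plan has no all-vaccinated safety set, so anyone given study vaccine without being randomised would be counted in none of the Section 5.4 safety tables

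*SAP*

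**What the plan says.** Table 4 sets out the analysis sets. The FAS is "All randomized participants with at least one documented study vaccine and met inclusion criterion 1", and FAS7 is the part of the FAS still active when the site approves PA7. The table has no separate safety set and no set of all vaccinated participants.

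Section 5.4 opens with the rule "All safety analyses will be performed on the FAS or FAS7". Section 4 agrees for both the active and the passive follow-up. Section 5.4.4 adds: "All safety analyses will be tabulated by vaccination group according to the *as treated* principle".

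Section 5.1.3 lists disposition categories, among them "participants vaccinated at day 1 and not randomized" and "participants randomized, not vaccinated at day 1".

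The vaccination groups are described twice. In Section 1.2 (the list after Table 2) the placebo group is "Participants who were randomized and first vaccinated with Placebo until they received any other active COVID-19 vaccine" and the active group is "Participants whose first active vaccination is Ad26.COV2.S". In Section 5.4.4 the placebo group is "All participants who received as first vaccination a placebo injection".

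**The concern.** Descriptive safety tables grouped by vaccine received are normally meant to cover everyone exposed. Here, entry also requires randomisation. That condition would matter if the tables compared randomised arms, but Sections 5.1 and 5.4 plan neither group comparisons nor formal testing of safety data. The condition therefore protects no contrast; all it can do is leave out exposed people.

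Section 5.1.3 shows that the authors foresaw vaccination without randomisation, at least as a reporting category. What is at stake is completeness for very rare events. The plan tracks such events: thromboembolic events close in time to thrombocytopenia (Section 5.4.6.1) and Guillain-Barré syndrome (Appendix 6). For these, one case more or less can be seen in a table.

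**Working it through.** **Set membership**

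1. FAS = randomised AND at least one documented study vaccination AND inclusion criterion 1 met (Table 4).
2. FAS7 = FAS AND still active at PA7 site approval (Table 4).
3. Population for the 5.4 tables = FAS or FAS7 (Sections 4 and 5.4).
4. A person who was vaccinated but not randomised fails the first condition of step 1, so is in neither set and enters no numerator or denominator in 5.4.

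Participants newly enrolled in the open-label phase are not the issue: Section 1.2 has them randomised to one or two doses, so they can be in the FAS.

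**Possible exceptions**

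- Section 5.4.6.1 plans an overall summary for the whole study, described by receipt of at least one Ad26.COV2.S dose. It names no wider set and lies within Section 5.4, so the FAS/FAS7 rule appears to apply. It would not cover placebo-only recipients in any case.
- Section 5.4.6.2 provides listings or narratives, as appropriate, for deaths, serious events and discontinuations due to an AE. These might show an individual event, but they are not tables.

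**Size**

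The number of people affected, m, is not given and may be 0. Table 2 gives about 15,000 per group. The Ad26.COV2.S safety group also takes in placebo recipients who later received Ad26.COV2.S (Section 5.4.4), so N for that group is taken as 15,000 to 30,000.

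The largest shift in a percentage, with all m omitted people having the event, is m/(N+m):

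| m | N = 15,000 | N = 30,000 |
|---|---|---|
| 1 | 1/15,001 = 0.0067 points | 1/30,001 = 0.0033 points |
| 10 (assumed upper case) | 10/15,010 = 0.067 points | 10/30,010 = 0.033 points |

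These bounds are for the large groups as a whole. Section 5.4.6.2 uses the denominator of each phase and group, and the group given Ad26.COV2.S after an outside vaccine (layout 1b) has no stated size. Where the denominator is smaller, the bound is larger.

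For a rare event, the Clopper-Pearson 95% interval per 100,000, before and after adding one omitted person who is a case:

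| N | Cases without | Interval | Cases with | Interval |
|---|---|---|---|---|
| 30,000 | 0 | 0 to 12.3 | 1 | 0.08 to 18.6 |
| 30,000 | 3 | 2.1 to 29.2 | 4 | 3.6 to 34.1 |
| 15,000 | 0 | 0 to 24.6 | 1 | 0.17 to 37.1 |
| 15,000 | 3 | 4.1 to 58.4 | 4 | 7.3 to 68.3 |

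On the rate scale, assuming 1 to 2 years of follow-up per person at N = 30,000, going from 0 to 1 case gives 1/30,000 to 1/60,000 per person-year, or 0.0033 to 0.0017 per 100 person-years.

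**Base of the 5.1.3 rows**

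The first sentence of 5.1.3 says participant information is shown for the FAS. If that also governs the list that follows, the row for people vaccinated but not randomised must be zero, and the row for people randomised but not vaccinated on day 1 could hold only those first vaccinated later. But the list has its own introductory sentence and includes rows for the FAS and for randomised participants. On an FAS base both would be 100%, which suggests that a wider base was intended. The text does not settle which.

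**The case against.** The strongest reply is that randomised-and-vaccinated is a coherent choice. The as-treated principle decides which column a participant falls in; it does not decide who is in the population. That is right: the plan does not break its own as-treated rule. What remains is that the condition has no use in tables without comparisons, while it can leave out exposed people.

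A second reply is that the category may be empty, the analysis is descriptive, and listings or narratives may show the serious events. All of this stands, and it is why the point is minor.

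Three stronger readings are tempting, and the document does not support them:

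- *Sections 1.2 and 5.4.4 define conflicting groups.* Section 1.2 mentions randomisation for placebo only, and 5.4.4 for neither group. But the opening rule of 5.4 already limits both to randomised participants. The extra words in 1.2 are redundant, and nobody changes group.
- *The 5.1.3 row is zero by construction.* This holds only if the FAS is the base of the list, and the list's own rows suggest otherwise.
- *Exposed participants or their events have been lost.* The SAP gives no count and does not show that any such person exists.

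It is also fair to say that the remedy below does not reach literally everyone exposed. It keeps inclusion criterion 1, whose content this document does not state. And because Section 5.4.1 describes data collection only for the FAS, any people added may have incomplete follow-up.

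**Conclusion.** The point holds as a minor one. With FAS and FAS7 as the only safety populations, a participant vaccinated without randomisation would be absent from the 5.4 tables, apparently including the overall summary of Ad26.COV2.S recipients.

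The effect on percentages in the large groups is negligible. It becomes visible only if such a person exists, had safety data recorded and had a very rare event, and then it amounts to one more case. The conclusion rests on the Section 5.4 rule governing every table in that section, and the sizes rest on group totals of about 15,000 to 30,000.

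**What to change.** - In Section 4 and Section 5.4, define the population for the safety tables as all participants who met inclusion criterion 1 and have at least one documented study vaccination, randomised or not, grouped by vaccine received, where safety data were recorded. For the passive phase, use the part of that set still active at PA7 site approval.
- Say explicitly that the overall summary in 5.4.6.1 uses this population.
- In 5.1.3, state that the disposition rows are based on enrolled or vaccinated participants, so that the row for people vaccinated but not randomised can report a real count.
- As a consequential edit, drop the reference to randomisation from the placebo group in 1.2.
- Leave the efficacy risk sets on the FAS.

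The cost is wording in four sections, one population flag and a footnote. Phase derivation needs no change: where the first vaccination time is missing and cannot be taken from randomisation, Section 5.4.3 already sets it to 00:00. The downside is that the safety N may differ from the FAS N by a few, and the footnote should note that follow-up for anyone added may be incomplete. If nobody was vaccinated without randomisation, the safety tables do not change.

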## 5. STATISTICAL ANALYSES

### 5.1. General Considerations

No efficacy evaluations nor group comparisons will be done in the open-label part of the trial. The data will not fit the purpose of comparing groups.

Efficacy endpoints and safety data will be presented descriptively as the number of cases or safety events and as incidence rates per 100 person years of follow-up within the relevant period per vaccination group.

The vaccination groups presented in the safety analysis and in the efficacy analysis differ. Details for the safety analysis are presented in Section 5.4 and for the efficacy analysis are presented in Section 5.2 and Section 5.3.

#### 5.1.1. Scope of Analysis of the Open-Label Active Follow-up Phase

##### 5.1.1.1. Setting

###### *Unblinding due to availability of other authorized/approved COVID-19 vaccines*

In the double-blind phase of the study, investigators may receive requests to unblind study participants who become eligible to receive other COVID-19 vaccines if/when these are authorized/licensed for use. In these cases, the investigator will discuss with the participant available options and ramifications, including whether they are eligible to receive the Ad26.COV2.S vaccine in the study during the unblinding study visit. If the participant is eligible for a licensed vaccine according to local immunization guidelines or recommendation and if the participant wishes to proceed with the unblinding, the investigator will follow the unblinding procedures. The reason for the unblinding request should be documented. The name and date(s) of administration of the other COVID-19 vaccine should be recorded.

Participants who opt for enrollment in an Expanded Access Program or a Phase 3b study (eg, Sisonke/TOGETHER in South Africa) may be unblinded upon their request and will be encouraged to continue in the VAC31518COV3009 study.

When unblinding, if it is determined that the participant received the Ad26.COV2.S vaccine (and not placebo), the participant will be informed that there are no data on the safety of receiving two different COVID-19 vaccines and no further study vaccination would be permitted in the event he/she chooses to receive the vaccine outside the study. Unblinded participants, whether in the vaccine or control group, will be asked to continue to be followed in this study in line with the schedule of activities. Safety, efficacy, and immunogenicity evaluations will be identical for all participants, including participants that are unblinded to obtain an authorized/licensed COVID-19 vaccine and who remain in the study.

### ***Unblinding due to cross-over for Janssen Vaccine***

Section 6.4 from the latest protocol details the procedures to unblind participants at the Unblinding visit and offer participants who received placebo a single dose of Ad26.COV2.S vaccine.

If participants decide to continue the study at the Unblinding visit, participants will continue to be followed up and data will be collected as detailed further below.

As the study was still ongoing and recruiting new participants, there are 3 scenarios that could happen after approval of Clinical Trial Protocol Amendment 4 (CTPA4) which introduced cross-over vaccination and when the open-label unblinding visit occurs:

1. New participants that are enrolled after CTPA4 approval will go directly into the open-label phase of the study and will be included in the analysis of the open-label phase.
2. Already enrolled participants who have their open-label unblinding visit after receiving their 1st vaccination but before getting their 2nd vaccination will be included in the analysis of the open-label phase. All data (including data from the double-blind phase) will be included in the analysis of the open-label phase of the study.
3. Already enrolled participants who have their open-label unblinding visit after receiving both vaccinations will be included in the analysis of the open-label phase. All data (including data from the double-blind phase) will be included in the analysis of the open-label phase of the study.

### ***Booster Vaccination***

Section 6.5 from the latest protocol details the procedures to offer participants who received only a single vaccination with Ad26.COV2.S a single booster dose of Ad26.COV2.S vaccine ( $5 \times 10^{10}$  vp). Participants who already received 2 vaccinations with Ad26.COV2.S at the  $5 \times 10^{10}$  vp dose level or any COVID-19 vaccinations outside the study (including the Janssen vaccine) at the time of local approval of Protocol amendment 6 are not eligible to receive a booster vaccination with Ad26.COV2.S. The booster vaccination will be administered in the open-label phase of the study, preferably within 6 to 12 months after the participant's first Ad26.COV2.S vaccination in the study. If this is not possible, the booster vaccination should not occur earlier than 3 months after the participant's first Ad26.COV2.S vaccination.

